10.3 Analysis of Laboratory Data

10.3.1 Variables and Units

All laboratory parameters to be collected in this study are listed below. Laboratory parameters will be reported using the standard international (SI) units.

Table 10. List of Laboratory Variables

Laboratory Variables
Hematology
White Blood Cell (WBC) Count
Red Blood Cell (RBC) Count
Hemoglobin
Hematocrit
Platelets count
Neutrophils
Basophils
Eosinophils
Lymphocytes
Monocytes
Bands
Chemistry
Total Bilirubin
Alkaline Phosphatase (ALP)
Aspartate aminotransferase (AST)
Alanine aminotransferase (ALT)
Total Protein
Albumin
Glucose
Triglycerides
Blood Urea Nitrogen (BUN)
Creatinine
Uric acid
Sodium
Potassium
Calcium
Inorganic Phosphorus
Creatine Phosphokinase (CPK)
Chloride
Bicarbonate

Table 10. List of Laboratory Variables (Continued)

Laboratory Variables
Chemistry (Continued)
Cholesterol
LDL cholesterol
HDL cholesterol
LDL/HDL ratio
Cholesterol/HDL ratio
Urinalysis
Specific Gravity
pH
Protein
Glucose
Ketones
Blood
Microscopic Examination (if needed)
Urobilinogen
Bilirubin
Leukocytes
Nitrites
Other
hs-CRP
QuantiFERON-TB Gold ^a
ESR

a. For annual follow-up QFT is captured only for those with negative QFT at Screening.

10.3.2 Analysis of Laboratory Data for Period 1

The laboratory data will be summarized by the "as treated" treatment groups (Upadacitinib 15 mg QD and placebo group).

10.3.2.1 Assessment of Mean Change from Baseline and Percentage Change from Baseline in Clinical Laboratory Variables

Analyses of continuous hematology, chemistry, and urinalysis variables which are measured longitudinally will be performed by visits and by treatment group. For each parameter at each visit, the following summary statistics will be presented for each treatment group: sample size, mean, standard deviation, minimum, median and maximum.

An ANOVA model with treatment as a factor will be used to compare change and percent change from baseline between different treatment groups for selected laboratory parameters. Mean difference from placebo and associated 95% CIs will be presented. The analysis applies to the following laboratory parameters of clinical interest: hemoglobin, platelets, lymphocytes, neutrophils, creatinine, creatine phosphokinase (CPK), LDL, HDL, the ratio of LDL to HDL, and total cholesterol.

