9.1.2 Handling for Missing Data and Intercurrent Event

Non-Responder Imputation (NRI) Approach

The NRI approach will handle data for binary variables as follows.

- Subjects who prematurely discontinue from study drug will be considered as non-responders for all subsequent visits after discontinuation.

- In addition, any subject with any missing value for binary variables at a specific visit will be treated as non-responder for that visit.

The NRI data handling will be used for the primary estimand (refer to Section 9.2.1) for binary variables.

As Observed (AO)

The AO data handling will not impute values for missing evaluations, and thus a subject who does not have an evaluation on a scheduled visit will be excluded from the AO analysis for that visit. Regardless of premature discontinuation of study drug, all observed data will be used in the analysis. The AO data handling will be used to facilitate the supplementary analysis for both binary and continuous variables (refer to Section 9.2.2 and Section 9.2.3 where the corresponding supplementary estimand for the primary and ranked secondary endpoints is described respectively).

Mixed Effect Model Repeat Measurement (MMRM)

The repeated measure analysis will be conducted using mixed model including observed data at all visits. For the MMRM analysis, data collected after premature discontinuation of study drug will be excluded. The mixed model includes the categorical fixed effects of treatment, visit and treatment-by-visit interaction, main stratification factors at randomization and the continuous fixed covariates of baseline measurement. An unstructured variance covariance matrix will be used. The parameter estimations are based on the assumption of data being missing at random and using the method of restricted maximum likelihood (REML). MMRM will be used for the primary estimand of continuous variables (refer to Section 9.2.3).

Longitudinal Analysis for Long-Term Efficacy: MMRM and Generalized Linear Mixed Model (GLMM)

The repeated measure analysis will be conducted using mixed model including AO measurements at all visits. MMRM will be used for continuous endpoints and GLMM will be used for binary endpoints. The mixed models will include the categorical fixed

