9.2.1 Primary Efficacy Analysis

The primary efficacy endpoint for regulatory purposes is ASAS 40 response at Week 14. The primary estimand is the difference in the proportion of AS patients who achieved ASAS 40 response at Week 14 and did not discontinue study drug by Week 14, comparing those who are randomized to the Upadacitinib 15 MG QD group and received study drug to those who are randomized to placebo and received study drug.

Analysis of the primary endpoint will be conducted on the FAS based on randomized treatment groups (Upadacitinib 15 mg QD and the placebo group). Point estimate and 95% CI using normal approximation will be provided for the response rate for each randomized treatment group. Comparisons of the primary endpoint will be made between Upadacitinib and the placebo group using the Cochran-Mantel-Haenszel (CMH) test adjusting for stratification factor of hsCRP level (\leq ULN vs. $>$ ULN). Point estimate, 95% CI using normal approximation and p-value for the treatment comparison will be presented. The nominal p-value constructed using the CMH test will be provided. The multiplicity adjusted (as described in Section 9.2.5) testing results (significant or not significant) will also be provided. For the primary estimand, NRI data handling as defined in Section 9.1.2 will be used. To facilitate the interpretation of the estimand, the number and percentage of non-responders for ASAS40 will be summarized into three categories:

1. Subjects who discontinue study drug by Week 14

2. Subjects who didn't discontinue study drug but missing Week 14 ASAS 40 measurements
3. Subjects with ASAS 40 measurements observed and on study drug at Week 14 but didn't meet ASAS 40 response criteria

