9.2.3 Key Secondary Efficacy Analyses

The key multiplicity adjusted secondary efficacy endpoints at Week 14 are:

1. Change from Baseline in Ankylosing Spondylitis Disease Activity Score (ASDAS(CRP));
2. Change from Baseline in MRI Spondyloarthritis Research Consortium of Canada (SPARCC) score (Spine);

3. Proportion of subjects with BASDAI 50 response (defined as 50% improvement in the Bath AS Disease Activity Index);
4. Change from Baseline in AS QoL;
5. Proportion of subjects with ASAS partial remission (PR) (defined as an absolute score of ≤ 2 units for each of the four domains identified in ASAS 40);
6. Change from Baseline in BASFI;
7. Change from Baseline in BASMI_{lin};
8. Change from Baseline in MASES (for subjects with baseline enthesitis);
9. Change from Baseline in WPAI (the overall work impairment due to SpA);
10. Change from Baseline in ASAS HI.

Additional key secondary endpoints are:

- ASAS 20 response at Week 14.
- Change from Baseline in MRI SPARCC score (SI joints) at Week 14.

For binary endpoints, frequencies and percentages will be reported for each randomized treatment group. The primary estimand is the same as that for the primary efficacy endpoint as defined in Section 9.2.1, except for the definition of the efficacy measurement. NRI data handling will be used to analyze the primary estimand.

Supplementary analysis using AO data handling will also be conducted. The corresponding supplementary estimand is the same as defined in Section 9.2.2 except for the definition of the efficacy measurement. To explore various missing data assumptions including missing not at random (MNAR), tipping point analysis will also be conducted for ASAS 20 at Week 14 and details of the analysis are outlined in Appendix E.

Point estimate and 95% CI using normal approximation will be provided for the response rate for each randomized treatment group. Treatment comparisons will be made between

upadacitinib and the placebo group using the Cochran-Mantel-Haenszel. The CMH test adjusts for the main stratification factor of hsCRP level (\leq ULN vs. $>$ ULN). Point estimate, 95% CI using normal approximation and the p-value for the treatment difference will be presented.

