For continuous key secondary efficacy endpoints, the estimand is the difference in mean change from baseline at Week 14 under the assumption that patients with missing data including those due to premature discontinuation of study drug can have their measurements at Week 14 predicted by their observed data and the observed data for other patients for their respective assessments during follow-up. The comparison is Upadacitinib 15 MG QD vs placebo for patients randomized and treated with at least one dose of study drug.

For the primary estimand of the continuous key secondary efficacy endpoints, statistical inference will be conducted using the MMRM model and the associated data handling as described in Section 9.1.2, with the main stratification factor of hsCRP level (\leq ULN vs. $>$ ULN). The LS mean and 95% CI will be reported for each randomized treatment group; the LS mean treatment difference and associated 95% CI and p-value will be reported comparing Upadacitinib with the placebo group.

The supplementary analysis for secondary continuous variables will be conducted on AO cases using the analysis of covariance (ANCOVA) model with treatment and the stratification factor of hsCRP (\leq ULN vs. $>$ ULN) as the fixed factor and the corresponding baseline value as the covariate. The corresponding estimand is the difference in the mean change from baseline in the efficacy endpoints at Week 14 regardless of premature discontinuation of study drug. The comparison will be the Upadacitinib 15 MG QD vs placebo for patients randomized and treated with at least one dose of study drug and have the efficacy measurement available at Week 14. To explore various missing data assumptions including missing not at random (MNAR), the tipping point analysis will also be conducted using multiple imputation (MI) as additional supplementary analysis. Details of the tipping point analysis are outlined in Appendix E.

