For binary endpoints, point estimate and 95% CI using normal approximation will be provided for the response rate for each randomized treatment group. Point estimate, 95% CI and p-value will be provided for the treatment comparison between Upadacitinib and the placebo group, where the 95% CI will be based on normal approximation and the p-value will be based on the CMH test adjusting for stratification factor of hsCRP level. Only the nominal p-value will be provided. NRI data handling will be used.

For continuous endpoints, the LS mean and 95% CI will be reported for each randomized treatment group. The LS mean treatment difference and associated 95% CI and p-values between Upadacitinib and the placebo group will be provided using MMRM model with fixed effects of treatment, visit and treatment-by-visit interaction, hsCRP level (\leq ULN vs. $>$ ULN) and baseline value as covariate. Only the nominal p-value will be provided.

For the ASAS components (the 4 components are Patient's Global Assessment of Disease Activity NRS score; Patient's Assessment of Total Back Pain NRS score; BASFI; Inflammation (mean of items 5 and 6 of BASDAI NRS scores 0 - 10)), supplementary analysis will be conducted using AO data handling. Analysis of covariance (ANCOVA) model will be employed with treatment and the stratification factor of hsCRP level (\leq ULN vs. $>$ ULN) as the fixed factor and the corresponding baseline values as the covariate.

For categorical (more than 2 categories) endpoints, number and percentage for each category will be provided for each randomized treatment group. P-value will be provided for the treatment comparison between Upadacitinib and the placebo group using the extended Cochran-Mantel-Haenszel test adjusting for stratification factor of hsCRP level (\leq ULN vs. $>$ ULN). Only the nominal p-value will be provided. No missing data imputation will be used.

[figure not shown]
Evaluation of structural changes in the spine will be explored in subjects who are participating in the low-dose CT scan sub-study using a scoring system for syndesmophytes. Analysis for this sub-study is described in Appendix G.

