Note: The input dataset is subject-level data, with variable RESP_VALUE denoting the subject's response status ("1" as responder and "0" as non-responder). TRTP denotes the treatment group and STRATA denotes the strata for a given subject.

Categorical endpoints with more than 2 categories

The extended Cochran-Mantel-Haenszel test is used to assess the association among a set of q -by- r tables, where r is the number of levels in the ordinal categorical endpoints. For the case of insomnia severity index (ISI) which has $r = 4$ levels, the extended CMH test is stratified by hsCRP level that has $q = 2$ strata. The analysis is to assess the association between treatment and ISI, adjusting for the hsCRP level.

The following PROC FORMAT declaration is to ensure that the ISI categories are properly ordered in the analysis.

```
/*PROC FORMAT to ensure that the ISI categories are correctly ordered*/  
proc format;  
  value ISICat  
  1 = "No clinically significant insomnia"  
  2 = "Subthreshold insomnia"  
  3 = "Clinical insomnia (moderate severity)"  
  4 = "Clinical insomnia (severe)";  
run;
```

Denote n_{hij} the number of subjects who are in hsCRP stratum h ($h = 1, \dots, q$), treatment group i ($i = 1, 2$) and have ISI category j ($j = 1, \dots, r$). Also suppose $\{a_{h1}, \dots, a_{hr}\}$ is a set of scores associated with each level of the response variable in stratum h . In this

analysis, we use the SAS default "integer scores" such that $\{a_{h1}, \dots, a_{hr}\} = \{1, \dots, r\}$ for $h = 1, \dots, q$.

The sum of strata scores for treatment $i = 1$ is

$$f_{+1+} = \sum_{h=1}^q \sum_{j=1}^r a_{hj} n_{h1j}$$

Under the null hypothesis of no association, f_{+1+} has the expected value and variance

$$E\{f_{+1+}|H_0\} = \sum_{h=1}^q n_{h1+} \mu_h = \mu_*,$$

$$V\{f_{+1+}|H_0\} = \sum_{h=1}^q \frac{n_{h1+}(n_h - n_{h1+})}{n_h - 1} v_h = v_*,$$

where $\mu_h = \sum_{j=1}^r (a_{hj} n_{h+j}/n_h)$ is the finite subpopulation mean and $v_h = \sum_{j=1}^r (a_{hj} - \mu_h)^2 (n_{h+j}/n_h)$ is the variance of scores for stratum h .

The extended CMH test statistic is

$$Q_{SMH} = \frac{(f_{+1+} - \mu_*)^2}{v_*}$$

which has an approximate chi-square distribution with one degree of freedom. The following PROC FREQ implements the test for ISI and the test statistics Q_{SMH} corresponds to "Row mean scores differ" in the output.

```
/*ORDER=FORMATTED is critical*/
proc freq data=ISI order=formatted;

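### The Period 1 laboratory comparison with placebo omits the baseline value as a covariate; it is valid, but its confidence intervals are wider than they need to be

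*SAP*

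**What the plan says.** SAP Section 10.3.2.1 covers haemoglobin, platelets, lymphocytes, neutrophils, creatinine, CPK, LDL, HDL, the LDL/HDL ratio and total cholesterol. Two outcomes, change and percent change, are modelled: "An ANOVA model with treatment as a factor will be used to compare change and percent change from baseline between different treatment groups". The output is an interval estimate: "Mean difference from placebo and associated 95% CIs will be presented". Neither the baseline value nor a stratification factor enters the model, and no reason is given.

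The continuous efficacy models differ. The general MMRM text in Section 9.1.2, repeated in Appendix D, includes "main stratification factors at randomization and the continuous fixed covariates of baseline measurement". The ANCOVA in Section 9.2.3 and the exploratory models in Section 9.2.4 also carry the baseline value.

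On stratification, the general MMRM text uses a plural and names no factor. The endpoint sections name one: the primary analysis is made "using the Cochran-Mantel-Haenszel (CMH) test adjusting for stratification factor of hsCRP level" (Section 9.2.1), the continuous key secondary analyses "with the main stratification factor of hsCRP level" (Section 9.2.3), and in Appendix C "the extended CMH test is stratified by hsCRP level". The code in Appendix D uses a variable STRATA without saying which factor it holds.

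**The concern.** Period 1 is the only placebo-controlled laboratory comparison in the study. Placebo subjects switch to upadacitinib at Week 14, and the later laboratory means in Section 10.3.3.1 are descriptive, by treatment sequence. The Period 1 mean difference and its CI are therefore the study's controlled estimate of the drug's average effect on haemoglobin, neutrophils, lymphocytes, creatinine, CPK and lipids. Several of these correspond to adverse events of special interest in Protocol Section 6.1.1.3 (anaemia, neutropenia, lymphopenia, renal dysfunction, CPK elevation).

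Subtracting or dividing by baseline is not the same as adjusting for it. A change score fixes the baseline slope at 1, whereas ANCOVA estimates it from the data. When the correlation is below 1, the change score carries avoidable variance. At stake is the width of a safety interval, not the validity of a test.

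**Working it through.** **Inputs.** The plan states no precision for the laboratory comparison, so there is no figure of that kind to reproduce. The arm size is 85 (Protocol Section 8.2: 170 subjects, 1:1). That size does reproduce for ASAS 40: 20% v 46%, 90% power, two-sided 0.05 and a continuity correction give 75 per arm, and 75/0.90 = 83.3, so 84 per arm, or 168 against the stated 170. The documents give no baseline-to-follow-up correlation (rho), standard deviation or coefficient of variation (CV) for any laboratory parameter. Those below are assumptions, shown as ranges.

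**Absolute change, equal SD (S) at baseline and follow-up.**
- Residual variance of the change score: 2(1 - rho)S².
- Residual variance under ANCOVA: (1 - rho²)S².
- Variance ratio: (1 - rho²)/[2(1 - rho)] = (1 + rho)/2. CI width ratio: its square root.
- Half-width at n per arm: 1.96 × sqrt(2 × variance/n), with n = 85.

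| Assumed rho | Half-width, treatment only (S) | Half-width, ANCOVA (S) | Width ratio | CI narrower by | Equivalent extra subjects, 2/(1 + rho) - 1 |
|---|---|---|---|---|---|
| 0.4 | 0.329 | 0.276 | 0.837 | 16% | 43% |
| 0.6 | 0.269 | 0.240 | 0.894 | 11% | 25% |
| 0.8 | 0.190 | 0.180 | 0.949 | 5% | 11% |
| 0.9 | 0.134 | 0.131 | 0.975 | 3% | 5% |

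A simulation with 85 per arm and 3,000 trials per cell (normal data, CV 10%) gave 16.1%, 10.1%, 4.8% and 2.2% narrower, in line with the formula.

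**Unequal SDs.** If follow-up SD is k times baseline SD, the variance ratio is k²(1 - rho²)/(1 + k² - 2·rho·k). For k of 0.8, 1 or 1.25 and rho of 0.5, 0.7 or 0.9, it runs from 0.57 (k = 0.8, rho = 0.5) to 0.98 (k = 1.25, rho = 0.7). The CI is then about 24% to 1% narrower. Apart from one degree of freedom, ANCOVA is not the less precise model in any of these cases.

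**Percent change.** The formula does not apply, so this was simulated on the same design (rho is on the log scale for the lognormal rows).

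| Assumed distribution | rho 0.4 | rho 0.6 | rho 0.8 | rho 0.9 |
|---|---|---|---|---|
| Normal, CV 10% | 16.4% | 10.4% | 5.0% | 2.3% |
| Lognormal, CV 30% | 13.7% | 9.0% | 4.4% | 2.0% |
| Lognormal, CV 80% | 6.8% | 5.2% | 3.0% | 1.4% |

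Entries are the percentage by which the ANCOVA interval is narrower. Coverage of the 95% CI was 94.2% to 95.7% for all models, with and without baseline, so the planned analysis is valid.

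**Stratification wording.** Sections 9.2.1, 9.2.3 and 9.2.4 and Appendix C all specify hsCRP alone. Section 9.2.3 says of its binary endpoints that "The CMH test adjusts for the main stratification factor of hsCRP level". Only the general text in Section 9.1.2 and Appendix D keeps the unnamed plural. Read together, hsCRP is the intended factor and the general text is loose.

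**The case against.** The strongest reply is that nothing here is wrong. Both models are unbiased under randomisation, and no p-value or decision rule hangs on the laboratory interval. Laboratory safety is also judged through shift tables, Grade 3 or higher counts and liver criteria (Sections 10.3.2.2 to 10.3.2.4), none of which uses this model. The size of the gain depends on correlations that the documents do not give, and at 0.8 to 0.9 it is only 5% to 3%. The Week 14 lock was in February 2019 (Section 11.0), so any change to those data is after the fact.

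All of that stands, and it limits the point to an improvement in precision. It does not remove it: the covariate is already in the database, the same SAP uses it for efficacy, and the interval was narrower on average in every case examined.

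A reader might also infer a second harm, that a chance baseline imbalance distorts the treatment-only difference. At 85 per arm, a one-SE imbalance is sqrt(2/85) = 0.153 SD and moves that difference by sqrt((1 - rho)/2) of its own SE, which is 0.55 at rho 0.4. But 0.55² = 0.30 = 1 - 0.837². This is the same variance loss in another form, and the planned CI already allows for it.

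**Conclusion.** The point holds as a minor matter of efficiency. The treatment-only laboratory ANOVA is valid. Adding baseline would narrow the CI for absolute change by about 16% to 3% for assumed correlations of 0.4 to 0.9 with equal variances. The gain for percent change is similar at low CV and falls to 7% to 1% for skewed parameters. No trial conclusion depends on it.

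Two stronger readings are not supported.

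- **Omitting region from the efficacy models is a material loss, or leaves two competing models.** Randomisation is stratified by hsCRP and region, and the SAP gives no reason for using hsCRP alone. But it does so consistently in the endpoint sections. In simulation (20,000 trials per scenario; assumed 70% above the hsCRP limit; US-Canada/Japan/RoW 25/8/67%), power of the primary CMH test was 95.6% to 96.3% with hsCRP alone and 95.6% to 96.5% with six strata, with type I error of 4.8% to 5.2% either way. For continuous endpoints, adding region narrowed CIs by between -0.1% and 2.3% (a negative value is a slight widening). Region is not free either: 11% to 12% of simulated trials had a stratum empty in one arm. What remains is the wording in Section 9.1.2 and Appendix D.
- **The unstratified Wald interval in Appendix C is wrong beside a stratified test.** Its simulated coverage was 94.3% to 95.1%, and it estimates the difference in proportions that Section 9.2.1 defines.

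**What to change.** In SAP Section 10.3.2.1, replace the treatment-only ANOVA with ANCOVA including treatment and the baseline laboratory value, for both change and percent change. For the locked Week 14 data, report it alongside the planned analysis and label it supplementary.

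In Section 9.1.2 and Appendix D, replace the unnamed plural with the factor in the model that was run (hsCRP, according to the endpoint sections, after checking the Week 14 program), and define STRATA as hsCRP level. No region-stratified or region-adjusted analyses are needed, at Week 14 or in the long-term models, because no material gain is shown.

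The cost is SAP wording, one covariate in the laboratory program and one extra set of supplementary estimates. No new data are required, and the pre-specified Week 14 efficacy analyses are unchanged.

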10.3.2.2 Assessment of Shift from Baseline in Clinical Laboratory Variables

The baseline and post-baseline laboratory observations will be categorized as Low, Normal, and High according to normal ranges. The shift tables will tabulate the number and percentage of subjects with baseline and post-baseline values by these categories.

For each laboratory variable, shift tables will be generated that cross tabulate the subjects' as deemed appropriate by treatment groups:

- Shift from baseline high or normal to minimum post-baseline low; shift from baseline low or normal to maximum post-baseline high.
- Shift from baseline high or normal to final post-baseline low; shift from baseline low or normal to final post-baseline high.

Note that the minimum/maximum category is used, rather than the category of the minimum/maximum value. The two may be different due to variation in the reference range.

No statistical tests will be performed for this analysis.

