8.1.5.3 Analysis of Laboratory and Vital Sign Data

Changes from baseline by visit; changes from baseline to minimum value, maximum value, and final values in continuous laboratory data; and vital signs will be summarized by treatment group.

Baseline values are defined as the last non-missing measurements recorded on or before the date of the first dose of study drug.

The laboratory data will be categorized as Grade 1, Grade 2, Grade 3, Grade 4, or Grade 5 according to CTCAE criteria. The shift tables will tabulate the number and percentage of subjects with baseline and post-baseline values by grade levels.

Summary and listings will be provided for potentially clinically significant laboratory values and vital signs.

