10.2.1.6 Adverse Events of Special Interest

The Adverse Events of Special Interest (AESI) categories will be summarized and presented by treatment groups using SOC and MedDRA PT. The AESI categories will be identified by the following search criteria per Standard MedDRA Queries (SMQs)/Company MedDRA Queries (CMQs) in [Table 9](#) below. Adjudicated

cardiovascular events will be summarized and presented by treatment group using the CAC adjudicated categories.

Table 9. AESI for Upadacitinib with SMQs/CMQs/PTs Searches

AESI	Type of MedDRA Query	Broad or Narrow Search	SMQ/CMQ Search Criteria
Serious Infections	CMQ		"Infections" – Subset for SAEs
Opportunistic Infection excluding Tuberculosis and Herpes Zoster	CMQ		"Opportunistic Infection excluding Tuberculosis and Herpes Zoster"
Possible Malignancy	SMQ	Narrow	"Malignancies"
Malignancy	SMQ	Narrow	"Malignant tumours"
Non-Melanoma Skin Cancer (NMSC)	SMQ	Narrow	Skin Malignant tumours (narrow SMQ) removing Melanoma CMQ
Malignancy excluding NMSC			"Malignant tumours" Narrow SMQ removing NMSC output
Lymphoma	SMQ	Broad	"Malignant Lymphomas"
Hepatic Disorder	SMQ	Narrow	"Drug Related Hepatic Disorders"
Adjudicated Gastrointestinal Perforations	Based on adjudicated results (the identification of events to be adjudicated are described in the GI Perforation charter)		
Anemia	CMQ		"Non-Hemolytic and Non-Aplastic Anemias"
Neutropenia	CMQ		"Hematological Toxicity – Neutropenia"
Lymphopenia	CMQ		"Hematological Toxicity – Lymphopenia (Veliparib Product Specific)"

Table 9. AESI for Upadacitinib with SMQs/CMQs/PTs Searches (Continued)

AESI	Type of MedDRA Query	Broad or Narrow Search	SMQ/CMQ Search Criteria
Herpes Zoster	CMQ		"Herpes Zoster"
Creatine Phosphokinase (CPK) Elevation	PT		Search only for the PT of "Blood creatine phosphokinase increased"
Renal Dysfunction	SMQ	Narrow	"Acute Renal, Failure"
Active Tuberculosis	CMQ		"Active Tuberculosis"
Adjudicated Cardiovascular Events	Output from CAC		
MACE*			
Undetermined/Unknown Cause of Deaths			
Other Cardiovascular events			
Adjudicated Thrombotic Events	Output from CAC		
Venous Thromboembolic Events**			
Other Venous Thrombosis			
Arterial Thromboembolic Events (non-cardiac, non-neurologic)			

* MACE; Major Adverse Cardiovascular Events, defined as cardiovascular death, non-fatal myocardial infarction and non-fatal stroke.

** Venous thromboembolic events (VTE) include deep vein thrombosis (DVT) and pulmonary embolism (PE).

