10.3.2.3 Assessment of Potentially Clinical Significant Laboratory Values

The criteria for potentially clinically significant laboratory values will be determined by CTCAE criteria of Grade 3 or higher. The number and percentage of subjects meeting the criteria for potentially clinically significant laboratory values will be summarized by "as treated" treatment group.

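### SAP 10.3.2.2 replaces the protocol's CTCAE-grade laboratory shift tables with Low/Normal/High shifts without recording the change, so Grade 1-to-2 worsening and baseline grade are lost

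*SAP*

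**What the plan says.** Protocol 8.1.5.3 sets the categories: "The laboratory data will be categorized as Grade 1, Grade 2, Grade 3, Grade 4, or Grade 5 according to CTCAE criteria". It then sets the table: "The shift tables will tabulate the number and percentage of subjects with baseline and post-baseline values by grade levels".

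SAP 10.3.2.2 uses the reference range instead: "The baseline and post-baseline laboratory observations will be categorized as Low, Normal, and High according to normal ranges". For the extreme value it lists: "Shift from baseline high or normal to minimum post-baseline low; shift from baseline low or normal to maximum post-baseline high". For the last value it lists: "Shift from baseline high or normal to final post-baseline low; shift from baseline low or normal to final post-baseline high". The tables are descriptive, with no tests.

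The SAP keeps CTCAE grading for one other Period 1 output, in 10.3.2.3: "The criteria for potentially clinically significant laboratory values will be determined by CTCAE criteria of Grade 3 or higher". The long-term laboratory section (10.3.3) has Grade 3 or higher counts and listings but no shift table.

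SAP 3.0 describes the document as elaborating the protocol's methods. The version history in SAP 12.0 does not name a change to the shift tables.

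**The concern.** The two documents specify different safety tables, and the SAP version carries less information. Low/Normal/High has one abnormal level in each direction. A subject who is Low at baseline and falls further stays Low, and a subject who is High and rises further stays High. Neither is among the listed shifts.

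Such subjects can enter. Exclusion criterion 28 bars hemoglobin only below 10 g/dL and AST or ALT only above 2 × ULN, and it sets no CPK limit.

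The variables matter for this drug. Anemia, neutropenia, lymphopenia and CPK elevation are adverse events of special interest (AESIs) in protocol 6.1.1.3, and protocol 3.2 reports trends to lower red and white cell counts. Period 1 is the only placebo-controlled comparison, so a categorical difference in mild-to-moderate worsening can be seen against placebo only there.

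**Working it through.** The plan gives no figure on this point, so there is none to reproduce. The check is which output counts each kind of worsening.

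**Assumption.** CTCAE thresholds are not in the documents. Take Grade 0 as within the normal range and Grade 1 or more as outside it. Consider one direction for one variable, Grades 0 to 4.

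**Number of worsenings.** Five grades give 5 × 4 / 2 = 10 possible moves to a higher grade.

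| Baseline → worst grade | Protocol grade table | SAP listed shift | SAP Grade 3 or higher count |
|---|---|---|---|
| 0→1, 0→2 | separate cells | counted, merged | no |
| 0→3, 0→4 | separate cells | counted, merged | yes |
| 1→2 | own cell | no | no |
| 1→3, 1→4, 2→3, 2→4, 3→4 | separate cells | no | yes, baseline grade not shown |

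- Protocol table: 10 of 10 shown.
- SAP listed shifts: 4 of 10, merged together; 10 − 4 = 6 missed.
- Of those 6, the Grade 3 or higher count includes 5.
- In neither SAP table: 6 − 5 = 1, the move from Grade 1 to Grade 2.

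Including Grade 5 leaves that last result unchanged, since any move to Grade 5 is also Grade 3 or higher. These are counts of transition types, not of patients.

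**Example from the documents' own limits.** An ALT of 1.5 × ULN is admitted. A rise to 2.9 × ULN is High to High, so it is not a listed shift, and it falls short of the first ALT multiple in SAP 10.3.2.4, which is 3 × ULN. It is in no categorical laboratory table, provided CTCAE Grade 3 does not begin below 3 × ULN.

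**How many subjects.** The share entering abnormal is not given. As an illustration only, for a variable where 5% to 30% enter abnormal in the relevant direction, 0.05 × 85 = 4.25 and 0.30 × 85 = 25.5, or about 4 to 26 per arm. That is the number who could not register a same-direction shift. The number who actually worsen and are missed is some unknown part of it.

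**The case against.** A reader might infer that the SAP hides the cytopenia and CPK signal, or removes the patients with least reserve. The documents do not support either reading.

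- The Grade 3 or higher count in SAP 10.3.2.3 has no baseline condition. A subject who starts low and reaches Grade 3 is counted.
- SAP 10.3.2.1 summarizes continuous hematology and chemistry by visit and arm. It also compares change from baseline with placebo, with 95% CIs, for "hemoglobin, platelets, lymphocytes, neutrophils, creatinine, creatine phosphokinase (CPK), LDL, HDL, the ratio of LDL to HDL, and total cholesterol". Subjects with abnormal baselines contribute. A mean does dilute worsening confined to a few subjects, and WBC, ALT and AST are not in that comparison.
- AESI tables by arm cover anemia, neutropenia, lymphopenia and CPK elevation (SAP 10.2.1.6). The cover is partial: under protocol 6.1.1.1 a laboratory change is an adverse event only if it leads to stopping study drug, needs treatment, or the investigator judges it one.

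A reader might also infer that these subjects are in no cell at all. SAP 10.3.2.2 speaks of cross-tabulating baseline and post-baseline categories, so a full 3 × 3 table is a possible reading. It would not restore the information, because a Low-Low or High-High cell cannot separate worsening from no change. The gap also concerns same-direction worsening only; a move from High to Low is listed.

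Finally, protocol 8.1 leaves analysis detail to the SAP. That allows elaboration, but it does not explain replacing a table the protocol specifies.

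**Conclusion.** The protocol and SAP disagree on the laboratory shift tables, and the SAP does not record the change. Severe worsening is still counted and mean changes are still compared. Apart from the liver multiples, the categorical laboratory tables lose three things:

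1. worsening from Grade 1 to Grade 2;
2. the distinction between Grade 1 and Grade 2 in shifts from normal;
3. the baseline grade behind each Grade 3 or higher count.

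The discrepancy stands on the text alone. The transition count rests on taking Grade 0 as within the normal range. The number of subjects affected cannot be derived from the documents. No efficacy inference is touched.

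**What to change.** In SAP 10.3.2.2, restore the protocol's table: baseline CTCAE grade by worst post-baseline grade, by treatment group. Apply it to the CTCAE-graded variables, at least hemoglobin, neutrophils, lymphocytes, platelets, WBC, creatinine, CPK, ALT and AST. Keep Low/Normal/High shifts for variables without grades.

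Add the same table for Any Upadacitinib at the Week 104 and final locks, using the baseline that SAP 10.3.3.2 already defines for that group. Protocol 8.1.5.1 plans safety analyses for the entire study as well as at Week 14.

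SAP 11.0 dates the Week 14 lock to February 2019, and SAP 4.4 makes that analysis unblinded. Any added Period 1 table should be labelled as a post-lock addition.

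The cost is a change of SAP wording and a few more descriptive tables. CTCAE grading is already needed for the Grade 3 or higher outputs, and no new data are collected.
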